- Treatment plans and delivery information
- Outcomes data
- Patient-reported quality of life questionnaires (if desired by the participating sites and approved by their Institutional Review Board (IRB)). See Appendix E for list of available health-related quality of life questionnaires.

The registry design including data collection forms were designed by a board of Clinical Advisors who are active users, including physicians, physicists, nurses and site administrators. The RSSearch® Patient Registry uses widely accepted standards for disease classification, treatment side effects and results and validated quality of life measures.

3 Objectives

Objectives of the RSSearch Registry include the following:

RSSearch® Patient Registry Protocol

Version Date: 7/19/2022 Version 1.1

- Allow participants to record information about usage of the SRS/SBRT/SFRT systems in everyday practice, including patient characteristics and disease information, treatment plans and outcomes
- Allow participants to record information useful for their own SRS/SBRT/SFRT business reporting including utilization
- Provide participants with ready access to data for publication of their own SRS/SBRT/SFRT experience and as a tool for establishing collaborations with other participating sites
- Facilitate quality improvement efforts for individual treatment providers
- Provide participants the opportunity to collect quality of life data and other patient-reported outcomes
- Understand the effectiveness of different treatment plans for different types of lesions, diseases and treatments
- Provide comparative patient outcomes data to facilitate appropriate and successful use of the SRS/SBRT/SFRT system
- Collect information that may be useful for reimbursement

The RSSearch® Patient Registry is not a clinical trial or study. It is listed on www.clinicaltrials.gov and described as an observational patient registry (ClinicalTrials.gov Identifier: NCT01885299).

Information entered into RSSearch is already being collected as part of the medical record for patients at participating sites.

4 Duration

The RSSearch® Patient Registry will be an ongoing effort. This Registry began in 2005, as the ReCKord CyberKnife Registry and these CyberKnife patients remain embedded in RSSearch.

5 Participants

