All clinical sites performing SRS/SBRT/SFRT treatment procedures of any kind will be invited and encouraged to participate in the Registry. Participation is voluntary, but Principal Investigators must be an active member of the Radiosurgery Society. There is no compensation for participation in the Registry, either to patients or to participating sites.

All sites participating in the Registry will be required to have a signed Data Use Agreement (DUA) or similar agreement with the Radiosurgery Society and submit this protocol to their Institutional Review Board (IRB) or Ethics Committee Review; this will expand the opportunities for collaboration and publication.

Sites will be required to comply with their own institution's IRB or Ethics Committee Review practices for ongoing review and approval.

Participating sites are responsible for sending the RSS Administrator documentation providing proof that they have received and/or have updated IRB or Ethics Committee Review approval.

6 Sponsorship

RSSearch resides under the auspices of the Radiosurgery Society and is funded partially through the membership fees of the RSS. An annual maintenance fee is required of all participants in RSSearch to cover costs for data storage, hosting fees, registry quality assurance (QA) and security checks.

The Radiosurgery Society® is a multidisciplinary non-profit organization aimed at advancing the science and clinical practice of radiosurgery. (See www.therss.org for additional information)

Objectives of the Radiosurgery Society® include:

- Improve results achieved in the field of Stereotactic Radiosurgery (SRS), Stereotactic Body Radiation Therapy (SBRT) and Spatially Fractionated Radiation Therapy (SFRT) by promoting scholarly exchange among the clinical users.
- Share detailed clinical information pertaining to SRS, SBRT and SFRT to promote protocol development.
- Encourage and enhance SRS, SBRT and SFRT techniques in the worldwide medical community and among healthcare providers and patients.

7 Patients

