All patients of any age who are screened for potential SRS/SBRT/SFRT treatment are eligible to be entered into the RSSearch Registry. Some basic information including referral source, disease location etc., will be entered for any *patient who is screened* for SRS/SBRT/SFRT System treatment. Additional detailed demographic, diagnostic, treatment plan and follow up data will be entered on *patients who are selected* for one or more of these treatments. Patients who are selected and treated with SRS/SBRT/SFRT approaches will have data about their health status collected over the long-term, as long as they are considered candidates for follow-up.

There are no specific inclusion/exclusion criteria. The RSSearch® Patient Registry does not require specific tests or measures. Data that is collected in the normal course of a patient's treatment and follow up are entered into RSSearch.

There are no established endpoints for the RSSearch (as there are, for instance, for a Clinical Study); however, specific measures are recorded before and after treatment to determine outcomes of various SRS/SBRT/SFRT treatment approaches for different diseases.

All prospective patients must sign or have signed an informed consent form prior to their data being entered into the RSSearch® Patient Registry.

Initial entry of retrospective patient data may be considered under a Waiver of Authorization.

A Waiver of Authorization may be applicable for the following reasons:

- Risk to subject privacy is minimal
 - Procedure data is de-identified via the use of a unique identification number (ID) that will be created and known only to the participating site
 - Only four of the 18 variables considered protected health information (PHI) are necessary for use of RSSearch, specifically dates (admission, discharge, service dates, date of death), age (birthdates not collected), zip code and patient e-mail address (collected only if an individual site and their respective patients wish to use the Patient Portal feature of RSSearch, and then the email is visible only to the participating site).
 - The dates are important for understanding the data including, if and when:
 - Any adverse events occurred during and after the procedure
 - Key cancer outcomes including survival

- If participating sites are using the Patient Portal feature, the patient e-mail will allow the patient to securely log-in to the Patient Portal and access and complete assigned quality of life questionnaires.

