- Obtaining informed consent from patients who have already had a procedure and may not be returning for follow-up at a treating center performing the procedure may not be practical
- Obtaining informed consent may also inhibit a participating site's ability to completely characterize their patient population over time, practices associated with use of their SRS/SBRT/SFRT systems and long term outcomes

Retrospective data is marked as such in the database and can be separated for data analysis and publication purposes.

If Informed Consent is not obtained for initial data entry of retrospective patients and if the patient returns for follow-up or if follow-up data is otherwise obtained, Informed Consent can be obtained at follow-up.

If practical, obtaining Informed Consent from both retrospective and prospective patients is highly encouraged.

8 Forms

The RSSearch Registry includes the following forms and is available upon request:

- Screening Form
- Treatment Plan Form
- Follow-up Form
- Quality of Life Questionnaires

The registry contains both required and optional data fields, but it is highly recommended that all data fields, including required and optional fields be entered into RSSearch.

Screening Form

On the Screening Form, information is entered about any patient who is screened for treatment.

A new Screening Form is initiated and used for:

- New patients who have not previously been treated with SRS/SBRT/SFRT
- Existing patients who have previously been treated with SRS/SBRT/SFRT and
 - Have a recurrence or need for additional treatment at a previously treated target location, or
 - Have a new target treatment location or locations
- Existing patients who have previously been screened, but not treated by SRS/SBRT/SFRT
- Patients who are screened and not selected for SRS/SBRT/SFRT

If a patient has more than one target treatment location that will be treated during a single treatment period, details on these individual treatment locations will be recorded on the Screening Form.

If patients are screened and *not* selected for SRS/SBRT/SFRT, some basic information is entered including treatment location, referring physician and the reason why one of these systems was not selected for this patient at this time.

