If patients are screened and selected for SRS/SBRT/SFRT treatment, the basic information mentioned above as well as the following additional information is entered; relevant patient characteristics and health status; detailed diagnostic information; and some information on reimbursement.

Treatment Plan Form

The Treatment Plan Form is filled out for every patient selected for SRS/SBRT/SFRT treatment. The design of the Treatment Plan Form follows typical treatment approaches, where a single treatment plan may be used to treat one or more lesions and multiple treatment plans may be used to treat a single target location. Clinicians will record one or more treatment plans and lesion details on a single Treatment Plan Form for any particular treatment period.

General Treatment Planning Systems (TPS) information can be digitally uploaded into RSSearch using an automated feature in VisionTree Optimal Care (VTOC) database platform (VisionTree, San Diego, CA, www.visiontree.com) the developer of the database platform used for RSSearch. This feature reduces the amount of duplicate data entry by participating sites while providing key information to meet the RSSearch Patient Registry objectives.

SRS/SBRT/SFRT systems not supported by system manufacturers may require manual entry of certain treatment planning information.

Treatment Plan Forms will be linked electronically within the database to patients, target treatment locations and lesions to assist with proper tracking for outcomes analysis.

Follow-Up Form

The Follow-Up Form is used to document the result of each treatment plan.

Follow-Up Forms are used at intervals determined appropriate by individual clinical sites. Data is recorded after patients attend regularly scheduled follow-up appointments. Patients are expected to be followed as long as they are deemed candidates for follow-up.

Follow-Up Forms will be linked electronically to patients and target treatment locations, lesions and treatment plans to assist with proper follow up and outcomes analysis.

Patient Quality of Life and other Patient-Reported Outcomes Forms

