The system requires all information that is transmitted across the Internet be encrypted via Hyper Text Transfer Protocol Secure (HTTPS). To help avoid unauthorized usage, an automatic log-off feature is utilized after an extended period of user inactivity. A role-based security model is implemented to restrict access to various segments of the system (i.e. reports, screens, and site-specific data, along with other identified restricted information). In addition, the user interface and application components are stored behind an industry standard firewall with all outside communication closed except HTTP, HTTPS and Virtual Private Network (VPN) communication, while the database is only accessible via the internal network and VPN access. The system is physically housed within a HIPAA compliant facility including network redundancy for data availability, 24/7 network monitoring, multilevel access control requiring Badge/Photo ID and biometric access screening, internal and external video monitoring, fire protection, and disaster and environmental controls. The server and network updates are managed by VisionTree. The system data is backed up daily.

10 Patient Confidentiality

A unique patient identification number created and known only to your participating facility should be utilized in RSSearch and not a Medical Record Number. This data field is considered a “private” field and available only to the clinical site entering that data. The patient identification number will be used only as required for registry operations, specifically:

- To assist in enabling the digital import of treatment plan data from various Treatment Planning Systems, automatically and accurately linking the data
- To assist in enabling the digital import of data currently being collected in electronic form by participating clinical sites
- To make it easier for individuals at participating clinical sites to find a specific patient to enter additional data, to modify previously entered data and to record follow up data

As an additional security measure, a randomly generated patient ID is generated by VisionTree and linked to the unique patient ID created by the individual sites. This randomly generated ID can be used by VisionTree and the RSS to communicate with you if necessary, about specific patients. See Section 9 above to see how the limited PHI entered into RSSearch will be managed and protected by the software application and services provided by VisionTree.

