Obtaining Patient Informed Consent for prospective patients being entered into the database is required and is highly suggested for retrospective patients; since increasingly, peer reviewed publications require Informed Consent for submitted research. A sample Patient Consent Form is attached in Appendix B. For institutions that require a patient research authorization to collect patient data prospectively, a sample Patient Authorization Form is attached in Appendix C.

14 Risks/Benefits

There are no specific risks to patients of having limited patient information collected in a central database. Information entered into RSSearch is currently being collected as a standard part of patient care and follow up.

The benefits may include improved follow up for individual patients by participating sites and improved understanding of the use and results of SRS/SBRT/SFRT treatment for all patients.

15 Reporting of Adverse Events

The RSearch® Patient Registry provides a means on the Follow-Up Form for participating sites to indicate if the patient is experiencing any unexpected side effects or adverse events (AE) that can be attributable to SRS/SBRT/SFRT treatment. Reported adverse events will be graded on a scale of 1-5 as defined by the published standard Common Terminology Criteria for Adverse Events (CTCAE) v5.

Participation in RSearch with its AE system does not in any way replace the responsibilities of clinicians or sites in reporting adverse events related to any treatment in accordance with all applicable laws and regulations including notifying the manufacturer of the associated SRS/SBRT/SFRT device, or medical complaints associated with SRS/SBRT/SFRT treatment as soon as possible.

16 Appendix A: Institutional Review Board (IRB) and Ethics Review Committee Considerations

Aspects to consider in determining what type of review (expedited or full board) application to use include:

1. The RSSearch® Patient Registry is not a clinical trial or study, and no investigational device exemption (IDE) is required for use of the various SRS/SBRT/SFRT Systems.
2. Data entered into RSSearch are observational outcomes data, which are already collected as part of the medical records for patients undergoing SRS/SBRT/SFRT treatment.
3. A unique patient identification number (not medical record number) is recorded at the site level, is only available to the respective site, and is used for the following purposes:

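### Section 15 can be read as limiting adverse event recording to unexpected events, so sites that read it narrowly would leave out expected treatment-related toxicity

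*Protocol*

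**What the plan says.** Section 15 (Reporting of Adverse Events) describes what the Follow-Up Form captures: it gives sites a means to "indicate if the patient is experiencing any unexpected side effects or adverse events (AE) that can be attributable to SRS/SBRT/SFRT treatment". The next sentence adds "Reported adverse events will be graded on a scale of 1-5", using CTCAE v5. 'Unexpected' is not defined anywhere in the protocol.

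Other sections touch on the same subject:

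- Section 7 (Patients) explains why dates are held, among other things to show if and when "Any adverse events occurred during and after the procedure".
- Section 8 (Forms) states the form's purpose: "The Follow-Up Form is used to document the result of each treatment plan". It also says "The RSSearch Registry includes the following forms and is available upon request"; the forms are not reproduced.
- Section 2 (Purpose) says that accepted standards are used for treatment side effects, without limiting these to unexpected ones.
- Section 3 (Objectives) includes: "Provide comparative patient outcomes data to facilitate appropriate and successful use of the SRS/SBRT/SFRT system". Section 12 and Appendix D provide for publication of aggregate data.

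**The concern.** Much of the toxicity of a treatment may be of a kind that clinicians anticipate. If 'unexpected' governs both nouns in Section 15, a site that follows it literally enters only the surprising events. Its record then understates treatment-related toxicity, although the registry is meant to support comparison of outcomes.

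The more awkward case is a mixture of readings. If some sites enter all attributable events and others only the unexpected ones, a pooled difference between treatments can arise from which sites gave which treatment. Section 10 rules out identified comparisons between physicians and between geographic areas, but not comparisons by treatment or disease, where this would show. Released aggregate data carry no site identifiers (Section 12, Appendix D), so an outside requester could not adjust for it. The society does receive site identity for study requests and quality assurance, but the protocol provides for no record of the reading that each site used.

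This is a rule about data collection. No analysis plan, whatever it contains, can restore events that were never entered.

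**Working it through.** The protocol states no toxicity rate, sample size or other figure on this point, so there is nothing to reproduce. The check is one of text, followed by a short derivation of direction.

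**Step 1: the two readings of Section 15.**

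- Narrow: 'unexpected' limits both side effects and adverse events. Expected attributable toxicity is not recorded.
- Broad: 'unexpected' limits side effects only. All attributable adverse events are recorded, expected or not.

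Both are grammatical. Attribution by the site is required under either, so it is not a source of the ambiguity.

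**Step 2: does other text settle it?**

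| Place | What it says | Leans to | Tells sites which events to enter? |
|---|---|---|---|
| Section 15, second sentence | grades reported events, without 'unexpected' | broad | No; it applies to events already reported |
| Section 7 | dates show if and when any adverse events occurred | broad | No; it is a reason for holding dates |
| Section 8 | the form documents the result of each plan | broad | No; it is a general purpose |
| Section 2 | accepted standards for side effects | broad | No; it concerns classification |

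All four lean the same way and none is an instruction on entry. The ambiguity therefore stays open, although the narrow reading fits poorly with the rest of the document.

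**Step 3: direction of the effect.** Let *f* be the share of patients at sites that read the sentence narrowly, and *e* the share of attributable toxicity that is expected. Suppose the true rate and *e* are the same at all sites. Then

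recorded pooled rate = true rate × (1 − *f* × *e*).

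For *f* and *e* between 0 and 1 the factor never exceeds 1, so site-attributed toxicity can only be understated. With *f* = 0 the factor is 1 and there is no bias.

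For two treatments A and B with the same true rate, the ratio of recorded rates is

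(1 − *f*_A × *e*) / (1 − *f*_B × *e*).

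With *e* above 0, this equals 1 only if *f*_A = *f*_B, that is, if both treatments were given at narrow-reading sites to the same extent. Otherwise a difference appears without any difference in harm.

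**Step 4: size.** The documents give neither *f* nor *e*. Any percentage would merely return the values assumed for them, so none is offered.

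**The case against.** The strongest reply is that the deciding document is not shown. Sites enter data on electronic forms. Appendix D has the Administrators create and edit those forms and coordinate training, and Section 8 strongly encourages sites to complete every field, optional ones included. If the form or the training already asks for expected toxicity, the sentence in Section 15 changes nothing in practice. This stands, and it makes the harm conditional.

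Section 15 is also worded as offering a means to indicate events. It forbids no other entries. A reader might infer that the protocol restricts recording to unexpected events, or that Sections 7 and 15 contradict each other. The documents support neither inference: the broad reading is open, and Section 7 gives a reason for holding dates, not a rule on which events to record.

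Toxicity capture can differ between sites for other reasons as well. No specific tests are required, some fields are optional, and each site sets its own follow-up intervals. Rewording one sentence will not by itself make pooled toxicity comparable. That is true, but it does not justify keeping an avoidable source of difference.

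Finally, the loss can be repaired in part. Section 10 foresees that sites return to a patient's record "to modify previously entered data and to record follow up data", and the optional questionnaires in Section 8 cover some symptoms. But the protocol does not ask sites to use either route to fill this gap.

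**Conclusion.** The point holds as an ambiguity in the sentence that governs adverse event capture. Nothing else in the protocol instructs sites to enter expected toxicity, and a site that applies 'unexpected' literally would under-record. For site-attributed toxicity the bias can only be downward. The size cannot be derived, and it is zero if all sites read the sentence broadly or if the form or training already asks for expected events.

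A reader might go further and conclude that pooled registry toxicity is in fact understated and not comparable between sites. That would require that some sites read the sentence narrowly, that neither form nor training corrects them, and that the missing events are not added later. The documents show none of these.

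This is a cheap improvement that is worth making, held with medium confidence because the form is not shown.

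**What to change.** 1. Check the Follow-Up Form and the training material first, to see whether either limits entry to unexpected events.
2. Whatever that shows, remove 'unexpected' as a condition in Section 15. For example: *The Follow-Up Form records side effects and adverse events attributable to SRS/SBRT/SFRT treatment, whether or not expected, graded 1-5 by CTCAE v5.* Align this with Section 7.
3. Edit the form, and mark the change date in the database, only if the form itself carried the restriction. If it was already broad, a marker would suggest a break in the data that never happened.

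Cost: one sentence, and possibly vendor work on the form and database. There may be some extra data entry at voluntary, uncompensated sites, taken from records they already hold. Sites must "submit this protocol to their Institutional Review Board (IRB) or Ethics Committee Review" and comply with ongoing review, so the amended text may need resubmission. It can go with the next protocol version, which the Administrators already distribute for that purpose (Appendix D). No test or visit is added.
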